#### Statistical Analyses for Behavioral Data

Differences in alcohol demand were analyzed using separate repeated measures analyses of variance (ANOVA) models for each demand index. In these models, condition was a two-level within-subjects factor (neutral, alcohol). Partial eta-squared was calculated as a measure of effect size. Subjective craving was similarly analyzed using a repeated measures ANOVA. A conventional significance level of  $p < .05$  was used for all analyses.

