Alcohol Demand	Alcohol Purchase Tasks-State Versions (e.g., “how many drinks would you consume right now if they cost \$3 each?”. All choices are hypothetical.)	REDCap
Alcohol Craving	Craving visual analog scales (e.g., three items assessing subjective alcohol craving; “How much do you want a drink?” “How high is your urge for a drink?” and “How much do you crave a drink?”; Rated from 0-100)	REDCap
Subjective Affect	Six 100-point affect circumplex items, from -50 to +50: Tense-to-Calm, Sad-to-Happy, Nervous-to-Relaxed, Bored-to-Excited, Stressed-to-Serene, and Depressed-to-Elated.	REDCap
Physiological Arousal	Blood pressure; heart rate	Electronic blood pressure monitor

Functional Magnetic Resonance Imaging (MRI) Scan

[figure not shown]
Participants will undergo a 60-minute fMRI scan at the Imaging Research Centre at SJHH on a research-dedicated 3-Tesla General Electric Discovery 750 MRI system. Scans will be administered by a licensed MRI technologist at the IRC.

1. Functional imaging will comprise T2*-weighted echo planar imaging scans with a gradient echo pulse sequence.
2. Structural imaging will comprise high-resolution T1-weighted fast spoiled gradient echo scan
3. Resting state functional connectivity scans will comprise T2*-weighted echo planar imaging scans with a gradient echo pulse sequence.

[figure not shown]
The in-scanner behavioural task is our fMRI alcohol demand paradigm (Alcohol Purchase Task; APT). A schematic depiction of the paradigm is presented in **Figure 1**. On each trial, participants are asked how many standard-sized drinks of their preferred alcoholic beverage that they would consume at a range of prices (e.g., “How many drinks would you consume if they cost \$4 each?”). Each run will comprise 22 trials in a randomized order. An important aspect of the paradigm is its fractionation of the choice process into two discrete units: a stimulus processing Consider period (4 sec) and an active selection Choose period (<6s). In the Consider epoch, participants process the drink price for that trial and mentally decide how many drinks they want to purchase. In the Choose epoch participants’ behaviorally select their consumption level. This permits dissociation of the cognitive processing part of the decision from the motor response of inputting the choice. The Consider period is considered the

primary period of interest. A jittered inter-stimulus interval (ISI) screen is presented in between trials (M = 8 sec, range 1-15sec)¹⁴.

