Figure 1. fMRI alcohol purchase task stimuli.
ISI = interstimulus interval, s = seconds

In this study, 4 runs of the paradigm will be administered (run duration = ~7 min). Each of the first two runs will be preceded by blocks of cues from one condition (either two runs of alcohol cues or two runs of neutral cues), and the final two runs will each be preceded by cues from the other condition. Example cues are presented in **Figure 2**. The order of cue conditions will be counterbalanced across participants.

The paradigm is programmed in E-Prime software and displayed via MRI-compatible stimulus presentation system. Participants make their responses using MRI-compatible button boxes. Specifically, participants use their dominant (more dexterous) right hand buttons to select the number of drinks and submit their choice by pressing a button with their left hand.

In addition to the APT, participants will complete a 9-minute resting state paradigm. During this scan, participants are asked to sit still with their eyes open (focusing on a fixation cross on the screen).

Breathalyzer Test & Urine Screen

Alcohol sobriety (i.e., breath alcohol concentration = 0.00%) at the beginning of the study visit will be assessed via a commercial breathalyzer device (e.g., Alco-Sensor; Intoxometers, Inc).

We will also assess recent drug use via a commercial urine drug screen (e.g., ToxCup 5-panel urine drug screen). Results of the drug screen will be recorded on the data sheet and kept strictly confidential. Collection of urine drug screen will follow laboratory SOPs.

VIII. Study Procedures

Participant Recruitment

Participants will be recruited from the Hamilton, Ontario community via advertisements/tear-off flyers posted on bulletin boards in public areas around Hamilton, such as libraries, university campuses, bus/train depots, grocery stores, etc. Flyers will also be posted on bulletin boards inside SJHH campuses. We will also post advertisements on online classified websites (e.g., Kijiji). We have also had success in prior studies with placing professional advertisements on Hamilton city busses and will use those methods as needed to increase recruitment.

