## Final Statistical Analysis Plan

### Data Analysis

#### Behavioral analyses.

Individual APT trials were coded according to the method used in MacKillop et al. (2014). Inelastic choices were choices for a participant's personal maximum consumption. Elastic choices were choices in which consumption was less than maximum but greater than zero. Suppressed choices were choices for no alcohol. Observed alcohol demand indices included Intensity (consumption at free price), Breakpoint (price that suppressed consumption to zero), and Omax (maximum expenditure). An exponentiated demand curve model (Koffarnus et al., 2015) was used to estimate  $\alpha$  for each participant's mean neutral and alcohol demand curves. A shared  $k$  parameter was calculated as the logarithmic range in consumption ( $k = 2.23$ ). A small number of outliers were winsorized for Omax (3 datapoints) and  $\alpha$  (3 datapoints) (Tabachnick and Fidell, 2001). Omax was square root transformed and  $\alpha$  was logarithmically transformed to correct for skew. Four participants did not reach breakpoint and were excluded from analyses using this index.

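### Scanner cue order is counterbalanced, but the demand ANOVA names condition only, so any shift between run pairs inflates its error term; a condition × order term removes this for one error df

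*SAP*

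**What the plan says.** Protocol section VII (Functional MRI Scan) describes four runs of the purchase task. The first two follow cues from one condition, "and the final two runs will each be preceded by cues from the other condition". It adds: "The order of cue conditions will be counterbalanced across participants". This is a two-sequence, two-period crossover.

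The SAP (Statistical Analyses for Behavioral Data) fits a separate repeated measures ANOVA to each demand index, with partial eta-squared as the effect size: "In these models, condition was a two-level within-subjects factor (neutral, alcohol". Craving is handled in the same way. Neither document names order, sequence, run pair or period as a model term.

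The SAP does not name the session that supplied the data. Its section on behavioral analyses says "Individual APT trials were coded" and estimates α "for each participant's mean neutral and alcohol demand curves". The protocol attaches the abbreviation APT to the scanner task ("The in-scanner behavioural task is our fMRI alcohol demand paradigm (Alcohol Purchase Task; APT"), so the scanner is the likely source. But Table 5 also lists "Alcohol Purchase Tasks-State Versions" for the laboratory cue exposure, where the protocol's appendix says order is typically fixed, neutral first.

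**The concern.** Within each participant, condition coincides with run pair. Practice, fatigue or habituation across four runs of 22 hypothetical choices would raise the alcohol-minus-neutral difference in one order and lower it in the other. Counterbalancing cancels this in the average, but a condition-only model leaves the spread between orders in the error term. The test is then less sensitive than the design allows, and partial eta-squared is lower than in a model that uses the assigned order. It is not miscalculated, because partial eta-squared depends on the model fitted.

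At stake are efficiency and reporting for the main behavioural contrast. Readers also cannot see how many participants had each order, the contrast within each order, or whether the four exclusions from the Breakpoint analysis upset the balance.

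**Working it through.** **Inputs.** From Protocol section VI (Sample Size): N = 70, f = .35, α = .05, power .80, and earlier cue effects of f = .44 to .56. Assumed: 35 per order, and f read as the standardised paired effect dz. The shift s is not in the documents, so a range is shown.

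**The plan's own figure.** For a paired contrast with noncentrality f²n and 69 error df, power at n = 70 is 0.823 and the smallest n for 0.80 is 67. With noncentrality f²(n − 1), power is 0.818. The stated N = 70 is therefore consistent with this kind of reading. If f is a within-factor f with correlation 0.5 (dz = 0.70), power is 0.9999, which does not resemble the stated figure.

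**Error variance.** Let D = alcohol minus neutral, with within-order SD σ, cue effect τ and run-pair shift π; s = π/σ.

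- Neutral first: mean of D = τ + π. Alcohol first: mean of D = τ − π.
- With equal orders, the overall mean of D still estimates τ, with true variance σ²/n.
- The condition-only error mean square has expectation σ²[1 + s²·n/(n − 1)]. At n = 70 and s = 0.5 this is 1 + 0.25 × 70/69 = 1.254. A raw-data simulation gave a ratio of 1.252.

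The true variance of the estimate is unchanged while its estimated variance grows, so the test is conservative.

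**Power and size.** Condition-only: the sum of squares is noncentral chi-square (69 df, noncentrality 70s²), independent of the mean, and power is integrated over it. Order-adjusted: noncentral t with 68 df and noncentrality dz√70.

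| s | Error multiplier | Power, dz .35 | Power, dz .44 | Power, dz .56 | Size of 5% test |
|---|---|---|---|---|---|
| 0 | 1.000 | 0.823 | 0.953 | 0.996 | 0.050 |
| 0.125 | 1.016 | 0.819 | 0.951 | 0.996 | 0.048 |
| 0.25 | 1.063 | 0.807 | 0.946 | 0.995 | 0.043 |
| 0.5 | 1.254 | 0.755 | 0.924 | 0.992 | 0.029 |
| Order-adjusted, any s | 1 | 0.823 | 0.952 | 0.996 | 0.050 |

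Condition-only power falls below 0.80 only when s exceeds about 0.30 (dz .35), 1.00 (dz .44) or 1.63 (dz .56). At dz = 0.70 it stays above 0.999 up to s = 0.5.

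**Precision and effect size at s = 0, 0.125, 0.25, 0.5.**

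- 95% half-width, t·√[(69 + 70s²)/69]/√70: 0.238, 0.240, 0.246, 0.267 SD; with the order terms, 0.239.
- Sample size with the same reported standard error, 70/(1 + s²): 70, 68.9, 65.9, 56.0.
- Population partial eta-squared at dz = .35, dz²/(dz² + 1 + s²): 0.109, 0.108, 0.103, 0.089; order-adjusted, 0.109.

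**Cost if there is no shift.** Power goes from 0.8231 to 0.8230 at dz = .35. The term breaks even at s of about 0.025.

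**Which term does the work.** In one simulated data set with s = 0.5, the within-subject error sum of squares on its df was 27.33 on 69 for condition only, 27.33 on 69 after adding an order main effect, and 24.64 on 68 after adding condition × order. Only the interaction changes the condition error term.

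**Breakpoint.** The SAP states: "Four participants did not reach breakpoint and were excluded from analyses using this index". Taking N = 70 − 4 = 66 and 33 per order, condition-only power at dz = .35 is 0.800, 0.796, 0.782 and 0.727, against 0.800 adjusted. If all four came from one order (35 against 31, probability 0.11 under random loss), the condition-only estimate is biased by (4/66)s = 0.061s, or 0.015 SD at s = 0.25.

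**Units.** If the shift is expressed instead in SDs of a single condition, as q, the multiplier is about 1 + q²/[2(1 − r)], where r is the neutral–alcohol correlation. At q = 0.5 this is 1.25, 1.42 and 2.25 for r = .5, .7 and .9.

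**The case against.** A condition-only comparison in a counterbalanced design is valid, and no error in the results is shown. The documents report no drift, and the protocol provides training on the scanner task beforehand, which could limit it. A material loss needs a shift that rivals the cue effect: at dz = .35 the threshold of 0.30 is about 85% of the planned effect (0.30/0.35), and at .44 and .56 it is more than twice the effect. The conversion dz = f is unverified, and under dz = 0.70 the power loss disappears. The data are already collected, the SAP does not plan confidence intervals, the primary aim is neural activity, and the scanner source is inferred. The order term does not remove carryover, which is the only order-related worry the protocol names, and it names it for the laboratory task.

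All of this stands as a limit on size and scope. It does not remove the point. The order allocation already exists, using it costs almost nothing if there is no drift, and it restores the planned precision if there is. Partial eta-squared, which the SAP does report, is affected whether or not intervals are given. The missing counts by order and the unnamed session do not depend on drift.

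**Conclusion.** The concern holds as an efficiency and reporting point. The stated model leaves any run-pair shift in the condition error term, multiplying it by about 1 + s². At the planning effect read as dz = .35, with 35 per order, the power loss is 1.6 points at s = 0.25 (0.823 to 0.807) and 6.8 points at s = 0.5 (0.823 to 0.755). There is no loss without a shift, and at dz = .44 to .56 the loss is at most 2.9 points up to s = 0.5. The estimate is unbiased with equal orders, and false positives become rarer. The size rests on an assumed s, on dz = f, and on the indices coming from the scanner task. If they came from the fixed-order laboratory task, the order adjustment does not apply.

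**What to change.** For demand indices from the scanner task, add an ANOVA with condition, order (alcohol first or neutral first) and condition × order, averaging the condition effect equally over the two orders. Keep the interaction whatever its p-value: at s = 0.25 it would reach significance only 54% of the time.

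- Because the SAP already contains realised values, label this analysis as order-adjusted, show it beside the condition-only result, and say which model each partial eta-squared comes from.
- Report the number per order for each index, including Breakpoint after its exclusions, and the alcohol-minus-neutral contrast within each order.
- State which session supplied the demand and craving data. Do not apply the order term to laboratory measures, where order is normally fixed.
- State that the order term does not remove carryover.

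The cost is SAP wording, one extra ANOVA for each of the four demand indices, and one error df (69 to 68, or 65 to 64 for Breakpoint if N = 66). Order was assigned by design and should be recoverable from run records, though the documents do not say where it is stored.
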